## 1. Specific Aims

- a) To determine perceptions of TBA involvement in postnatal care referrals among health care providers, TBAs, and mothers
- b) To define barriers and enablers of TBA involvement in postnatal care referrals
- c) To estimate the impact of performance-based monetary incentives to TBAs on postnatal care referrals of delivery clients
- d) To estimate heterogeneity in impact of performance-based monetary incentives to TBAs on postnatal care referrals of delivery clients

## 2. Background

### 2.1 Provide the scientific background and rationale for the study

The traditional birth attendant or TBA is a traditional, independent (of the health system), non-formally trained, and community-based provider of pregnancy-related care (WHO, 2004). TBAs often do not understand how to appropriately manage complications during child birth, so that mothers and neonates they care for are at higher risk of death from delivery complications relative to those cared for by skilled health workers (Itina, 1997). The World Health Organization recommends that the best role for the TBA is to serve as an advocate for skilled care (WHO, 2004). However, there are strong social norms of pregnant women patronizing the TBA for antenatal care and delivery services as TBAs are highly respected in their communities. The TBA is also paid for her services. Therefore, referring women to skilled health providers for antenatal and delivery care goes against the financial and social interests of the TBA. The pronouncement that TBAs are not part of the Nigerian health system has not changed patterns TBA patronage for antenatal and delivery care (Owens-Ibie, 2011).

In contrast to antenatal and delivery care, only 4 percent of Nigerian mothers receive postnatal care from a TBA indicating that there is potentially less competition between the TBA and skilled health workers after delivery for the high-risk mother (NPC and ICF International, 2014). Postnatal care within 48 hours of childbirth (early PNC) offers the opportunity for early detection of complications, prevention of mother to child transmission of HIV, and provision of other critical support, to reduce mortality risk. There is therefore the potential for partnerships with TBAs to be effective in increasing uptake of early PNC among Nigerian mothers, which in turn could reduce preventable mortality.

### 2.2 Describe the significance of the research, and how it will add to existing knowledge

There are few studies that explore the involvement of TBAs in referrals for postnatal care. There is also no experimental evidence on the effectiveness of performance-based incentives for TBA referrals in the postnatal period. We propose to conduct a mixed methods study on the engagement of TBAs for postnatal care demand-generation among their delivery clients (mother who are attended at delivery by the TBA). The qualitative study will involve focus group discussions with TBA delivery clients, TBAs, and skilled health workers, to clarify

perceptions about, barriers to, and enablers of TBA engagement in postnatal care referrals. Informed by a recently completed qualitative pilot study (there was no control group), we will also identify the causal impact of performance-based incentives in increasing postnatal care referrals by TBAs, via a randomized controlled trial (Oyebola, et al., 2014). The persistent high rates of non-facility births attended by TBAs across Africa imply that the findings of this study can broadly inform policy aimed at reducing preventable maternal and neonatal death on the continent.

### 3. Study Setting

#### 3.1. Identify the sites or locations where the research will be conducted.

The study will be conducted in approximately 67 purposively selected villages in South-Eastern Nigeria, in Ebonyi State. The intervention focuses on villages rather than health care facilities, as traditional birth attendants do not work from facilities and they are the focus of the intervention. We have not selected study villages at this point in the study and can add the full list as a modification – we need IRB approval to observe postnatal care to decide on villages with adequate facilities. We anticipate that at 1 facility per village, we will end up with at least 67 facilities. Some mothers will attend postnatal care in facilities outside their village as well though so that the full list of attended facilities cannot be obtained ex ante. It will be ascertained in the follow-up survey of delivery clients of traditional birth attendants.

The villages will be chosen such that:

1. there is a facility offering postnatal care within 1-hour walking distance of most households;
2. postnatal care practice in the facility involves routine visits within 24-72 hours, 7-14 days, and 42 days of delivery in line with national recommendations; and
3. the relationship between TBAs and health workers is sufficiently cordial to encourage partnership on postnatal care referrals.

A list of villages chosen for the study will be added as a modification.

#### 3.2. Describe the Principal Investigator’s experience conducting research at study site(s) and familiarity with local culture

The Principal investigator has worked on a number of health studies in similar contexts across Africa. These include “Financing the Delivery or Efficient, Effective, and Equitable Primary Health Care Systems in Africa” (PI: [name]); “Do Financing and Fathers Lead to Better Birth Preparedness and Safer Motherhood? Proposal for a Randomized Controlled Trial in Nairobi, Kenya” (PI: [name]); “Negotiating Delivery: Can Spousal Involvement Improve Maternal Health?” (PI: [name] and [name], Funders: Lab for Economic Applications and Policy); “Identifying Barriers to Investments in Health: Making the transition from biofuel to gas cooking in Ghana” (PI: [name], Funder: Harvard Sustainability Science Program); “Behavioral Economics and Demand for Maternal Health Services: A Series of Experiments in Kenya” (PI: [name] and [name]).

#### 3.3. Is the research conducted outside the United States?

No  Yes: If yes; describe site-specific regulations or customs affecting the research, local scientific and ethical review structure

We are required to obtain ethical approval from the the Research and Ethics Committee, Federal Teaching Hospital Abakaliki, prior to commencing data collection. Local ethical approval will be attached to the Harvard IRB application when it is obtained, and will cover all local implementing partners and local research staff in this study.

- #### 3.4 Are there any permissions that have been or will be obtained from cooperating institutions, community leaders, or individuals, including approval of an IRB or research ethics committee?
- No  Yes: If yes; provide a list of the permissions (also include copies with the application, if available)

We will obtain permissions from the following prior to implementation, which will be uploaded via a modification:

- a) Community heads of participating villages for access to community spaces
- b) State office of National Primary Health Care Development Agency for access to health care facilities
- c) Health Research Ethics Committee of the University of Nigeria Teaching Hospital, Enugu State for ethical approval of the study

#### 4. Study Design

##### 4.1. Describe the study design type

We will conduct a mixed methods study on the engagement of TBAs for postnatal care demand-generation among their delivery clients. The qualitative study will involve focus group discussions with TBA delivery clients, TBAs, and skilled health workers, to clarify perceptions, barriers, and enablers of TBA engagement in postnatal care referrals for non-facility births. We will also conduct a randomized controlled trial to identify the causal impact of performance-based incentives in increasing postnatal care referrals of TBA delivery clients.

##### 4.2. Indicate the study's duration - and the estimated date of study completion

We anticipate that the study will extend from 14 July 2016 to 31 May 2017, over 10 months and 18 days.

##### 4.3. Indicate the total number of participants (if applicable, distinguish between the number of participants who are expected to be screened and enrolled, and the number of enrolled participants needed)

The qualitative study will recruit up to 10 TBA delivery clients, health workers, and traditional birth attendants each, aiming for a minimum of 6 participants in each category who consent and join the focus group discussions.

The randomized controlled trial will screen 200 traditional birth attendants in all and requires a minimum of 160 TBAs to consent and enroll into the study as justified in the power calculations below. The total TBA enrollment for the study will not exceed 200. We expect that TBAs will deliver an average of 5 clients per month. We intend to survey each of these clients. Thus, over the 5-month intervention period, the randomized controlled trial team will approach up to 5000 TBA delivery clients (200 \*5\*5).

##### 4.4. List inclusion criteria

###### Focus Group Discussions

S/No	Group	Inclusion Criteria
1	TBA delivery clients	Mother beyond 42 days after culmination of first pregnancy, who have thus had the opportunity to choose to attend postnatal care given current policy recommendations; resident in community; was delivered by a TBA; willing to participate in study; over 18 years of age
2	TBAs	Resident in community; TBA role (on-formally trained, independent of health system, provider of pregnancy-related care) confirmed by village head; willing to participate in study

3	Health Workers	Involved in postnatal care delivery within formal health care system, precisely direct patient care; works in same community; willing to participate in study
---	----------------	---------------------------------------------------------------------------------------------------------------------------------------------------------------

Randomized Controlled Trial

TBAs will be identified as community-based providers of antenatal and/or delivery care, and who are non-formally trained. TBAs must be resident within the community, must not plan to relocate over the intervention duration, must be reachable via mobile phone, and will be identified in partnership with community leadership. They will be willing to participate fully in the study, including having their clients contacted to verify delivery details and postnatal care use.

All delivery clients of TBAs will be interviewed, that is women who gave birth assisted by TBAs (and reported by the TBA to the study team as described below).

We will conduct baseline surveys of facilities in potential villages in which the study will be conducted. These surveys will involve anonymized observations of random postnatal care visits to ascertain process quality of care received. Villages in which postnatal care is of adequate quality will be selected.

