### Randomized Controlled Trial

The primary outcome for this study is the proportion of delivery clients each TBA successfully refers for postnatal care within 48 hours of delivery.

The team will conduct postnatal care observation surveys in potential study villages. We will select villages that meet the criteria outlined in Section 3.1.

At baseline, trained enumerators will interview TBAs and complete a survey over 60 minutes in a private location chosen by the TBA. The information collected will include demographic data, stated motivation for services, description of services provided, and social network of the TBAs. We will make photo recordings of these interactions (between TBAs and enumerators) for the purpose of presentation as described below.

All TBAs that participate in the study will receive the following:

- Information on the study aims (attached to submission), the need for postnatal care attendance, and verbal encouragement to refer delivery clients to postnatal care within 48 hours of childbirth
- Offer of two-weekly cumulative payouts of \$0.70 per reported delivery they take that is verified by client.
- Each TBA will be assigned an identification number (TBA ID) and randomized with 50-50 probability to the referral incentive or control arm.

TBAs randomized to the referral incentive arm will also receive an offer of two-weekly cumulative payouts of \$2.00 per successful referral of delivery clients to early postnatal care in a facility if it is verified by the client. Delivery clients are women who have given birth assisted by the TBA. Verification is described below.

Thus, the required follow-up surveys will be conducted every two-weeks, consisting of:

- Self-reported deliveries by TBAs obtained via SMS messages sent by TBAs to the study team. TBAs will be asked to send a text message after each delivery they oversee. TBAs will text the name and contact details (phone number and address) of clients delivered over the past two weeks. Two-weekly calls will also be made by the study team to the TBAs to ensure that all deliveries are reported. Data to be recorded includes TBA name as well as TBA delivery client name, phone number, and address.

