- Calls to women who TBAs report they delivered (TBA delivery clients) – these calls will ascertain delivery by TBA, date of delivery, date and location of attendance of postnatal care (if attended), referral to postnatal care by TBA, incidence of delivery and postnatal complications. In these contexts, delivery of a child and where delivery occurs is often common knowledge. The TBA is often involved in the naming ceremony that holds soon after. The study team will nevertheless recruit TBAs who are willing to share this information and allow both TBAs and their clients to opt out of the study.
- For a random subset of mothers, we will back-check the facility attendance registers to confirm postnatal care attendance. We will attach approval for access to patient information as a modification.

The anticipated duration of the intervention is September 2016 to January 31, 2017.

As part condition for the receipt of one of the study grants (Women and Public Policy Program's Cultural Bridge Fellowship), the study coordinator will blog on field research activities related to both the focus group discussions and randomized controlled trials. These blogs will contain pictures of survey respondents or focus group participants, for which informed consent will be sought.

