**5. Data/Statistical Analyses Plan**

**5.1. Briefly describe the plan for data analysis (including the statistical method if applicable)**

Qualitative Data Analysis:

If carried out in Igbo, interviews will be translated to English language. All interviews will be transcribed verbatim in Microsoft Word, following which recordings will be destroyed. Transcription will ensure that grammar, sentence structure, pauses, and unfinished sentences are preserved as much as possible. Written notes will be expanded immediately after the discussions. For both written and recorded notes, we will label discussion inputs using pseudonyms as described above – all personal identifying information will be destroyed within one month of discussions. Finally, ahead of analysis, we will read each transcript and set of notes twice to ensure immersion within the dataset. Qualitative data will then be analyzed using thematic analysis to unearth themes salient in the group interviews. We will structure and depict these themes using thematic networks as described by (Attride-Stirling, 2001). The software for this analysis is NVivo.

Randomized Controlled Trial Data Analysis:

We aim to identify the intention-to-treat effect of incentives on the proportion of early PNC referrals of TBA delivery clients.

$$y_{ij} = \beta_0 + \beta_1 * T_j + X_{ij} + \varepsilon_{ij}$$

Where:

- $y_{ij}$  is the total proportion of referrals for TBA  $i$ , and village  $j$  of all her delivery clients;
- $T$  is a dummy variable indicating if the TBA is in the treatment arm;
- $X_{ij}$  is a set of baseline individual-level covariates;
- $\beta_1$  is the coefficient of interest and gives the average mean difference between the treatment and the control arms.

We will also identify interactions between incentives and baseline TBA characteristics (considered proxies for social preferences) in order to clarify pathways through which the intervention might have worked. I will specify a series of equations:

$$y_{ij} = \beta_0 + \beta_1 * T_j + \beta_2 * T_j * Var_{ij} + Var_{ij} + X_{ij} + \varepsilon_{ij}$$

Where:

- $Var_{ij}$  is a binary baseline characteristic for TBA  $i$  in village  $j$  previously included in  $X_{ij}$ ;
- $\beta_1$  is interpreted as the treatment effect when  $Var_{ij} = 0$ ;
- $\beta_2$  is the additional effect of  $Var_{ij}$

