### Randomized Controlled Trial Sample Size

Power calculations for this study are based on a comparison of proportion of TBA referrals for early PNC between 2 equal-sized arms for  $H_0=0$  against alternative that it is not. Qualitative evidence of a similar intervention in Nigeria was associated with an average of 5 facility referrals per recruited TBA per month (Akpan & Lah, 2012). The crude birth rate in Ebonyi State is approximately 42 births per 1000 population annually (NPC and ICF International, 2014). If 70 percent of mothers deliver at home, then TBAs can potentially deliver up to 29 births per 1000 population in a year. Thus, a total of 68092 births in Ebonyi State are eligible for referrals in a year, given the state population of 2.4 million (FMOH, 2011). There is an average of 3 TBAs per village and 30 villages per LGA. Thus approximately 90 TBAs work in each of the 13 LGAs in Ebonyi state (1170 TBAs in total). At an average of 60 deliveries per year (68092/1170), there are approximately 5 deliveries per month to each TBA. We have powered the study to detect a difference in proportion of referrals of 0.20, that is 1 extra referral/TBA/month given 5 deliveries. Assuming standard deviation in proportion of referrals equivalent to study by (Rai, 2014) of 0.37 and alpha of 0.05, a minimum sample size of 160 TBAs can detect this effect at the 5 percent level with 90 percent power. With 200 TBAs, we can detect this effect size with over 90 percent power at the 5 percent level. Given an average of 5 TBA delivery clients per month and 5-month intervention period, we expect to enroll at the minimum 4000 TBA clients. With 200 TBAs, we may enroll up to 5000 TBA clients.

The randomized controlled trial study procedures, analysis, and other aspects of the protocol will be registered with the American Economic Association's Registry for randomized controlled trials (<https://www.socialscienceregistry.org/>) prior to baseline data collection.

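### The primary proportion is measured only among clients the TBA reports after randomisation and the team then verifies; pay for an early attender differs by arm, and no analysis tests whether this selection matters.

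*Protocol*

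**What the plan says.** - **Who is counted.** Section 4.4 limits the trial's clients to "that is women who gave birth assisted by TBAs (and reported by the TBA to the study team as described below". Section 6.1 explains that these women must be identified after delivery and that the TBA is the only source. They are then telephoned and may decline (sections 6.1 and 14.1).
- **How they are reported.** Section 4.6: "TBAs will be asked to send a text message after each delivery they oversee". It also says "TBAs will text the name and contact details (phone number and address) of clients delivered over the past two weeks", and "Two-weekly calls will also be made by the study team to the TBAs to ensure that all deliveries are reported".
- **What is paid.** Both arms receive USD 0.70 (200 Naira) per client-verified delivery. The incentive arm also receives USD 2.00 (600 Naira) "per successful referral of delivery clients to early postnatal care in a facility if it is verified by the client" (sections 4.6 and 16.2).
- **What is checked.** Clients are called, and for a random subset of mothers "we will back-check the facility attendance registers to confirm postnatal care attendance" (section 4.6).
- **What is analysed.** Section 5.1: "We aim to identify the intention-to-treat effect of incentives on the proportion of early PNC referrals of TBA delivery clients". The SAP repeats this model and adds only the interaction models. Neither document plans a by-arm table of reported and verified clients, or any sensitivity analysis.
- **What is assumed.** Section 14.1 says that opting out by TBAs or clients does no harm if it is non-differential between arms and not frequent.

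**The concern.** Who enters each TBA's denominator is settled after randomisation, partly by the person being paid. In the incentive arm more money rests on an attender being reported with details that let the team reach her. The outcome is known within 48 hours, whereas reports and prompts can cover two weeks. Section 16.1 expects that some TBAs will escort or visit clients, so some will know who attended. Section 10.1 lets TBAs who notice a discrepancy have it resolved from facility registers; a disputed attendance is worth USD 2.00 in one arm and nothing in the other.

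If effort differs in this way, attenders are over-represented among verified incentive-arm clients and the estimated effect is too large. The planned checks would not show it. The reminder calls go to the same TBA, and the client calls and register checks reach only women already on the list.

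The condition in section 14.1 is also not enough if it is read as equal totals lost, because equal losses can differ in composition.

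**Working it through.** **Plan's figure.** Section 5.2 gives "of 0.37 and alpha of 0.05, a minimum sample size of 160 TBAs can detect this effect", with a difference of 0.20 and 90% power. n per arm = 2(1.960 + 1.282)² × 0.37² / 0.20² = 72, so 144 in total; 160 gives 92.8% power. The 160 is slightly generous and does not bear on this point. At 160, SE = 0.37 × √(4/160) = 0.0585, so a difference of about 0.115 reaches significance.

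**Pay.** Verified early attender: 0.70 + 2.00 = USD 2.70 (800 Naira) v USD 0.70 (200 Naira). Verified non-attender: USD 0.70 in both arms.

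**Bias model.** Assumptions, none of them in the documents: true early attendance p of 20% or 40% in both arms (no effect); every incentive-arm attender reported and verified; everyone else at a fraction f. With R = 1/f, a TBA with true proportion π shows Rπ/(Rπ + 1 − π).

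- If all TBAs share one rate and f = 0.70: 0.20/(0.20 + 0.56) = 0.263, bias +0.063; 0.40/(0.40 + 0.42) = 0.488, bias +0.088.
- TBAs vary, and that shrinks the bias, because a TBA at 0 or 1 does not move. Taking π as Beta, with 25 clients per TBA (5 a month for 5 months), the protocol's 0.37 implies a true between-TBA SD of 0.369 (p = 20%) or 0.364 (p = 40%).

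Bias = E[Rπ/(Rπ + 1 − π)] − p. Rejection rates come from simulated null trials: 80 TBAs per arm, mean 25 deliveries, coefficient of variation (CV) 0.5.

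| Everyone else at | SD | Bias, p = 20% | Bias, p = 40% | Trials with P < 0.05 |
|---|---|---|---|---|
| 90% | 0.37 (section 5.2) | +0.003 | +0.011 | about 5–6% |
| 90% | 0.20 (assumed) | +0.013 | +0.021 | about 6–9% |
| 70% | 0.37 (section 5.2) | +0.009 | +0.039 | about 6–10% |
| 70% | 0.20 (assumed) | +0.045 | +0.073 | about 23–48% |

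The 6% at SD 0.37 and 20% attendance cannot be told from the nominal 5%.

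**Equal losses, unequal composition.** At p = 20% and one common rate, lose 30% in both arms: all non-attenders in the incentive arm, unrelated to attendance in control. The result is 0.20/0.70 = 0.286 v 0.200. At the protocol's SD this shrinks to +0.011, or +0.075 at p = 40%.

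**Would a count comparison reveal it?** In the 70% case at p = 20%, verified counts differ by 0.76/0.70 − 1 = 8.6%. With CV 0.5 the relative SE is 0.5 × √(2/80) = 0.079, so power is about 19% (58% at CV 0.25).

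**Restoring unverified clients** (70% case, p = 20%, all loss at verification):

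- Not referred in both arms: 0.20 v 0.14, a difference of 0.06. At p = 40%: 0.40 v 0.28, or 0.12. At SD 0.37 these exceed the uncorrected +0.009 and +0.039.
- Incentive-arm ones not referred, control-arm ones at the TBA's observed proportion: 0.20 v 0.14/0.70 = 0.20, a difference of 0.
- Control-arm ones counted as referred: 0.20 v 0.14 + 0.30 = 0.44, a lower bound of −0.24.
- If the 30% loss were unselective in both arms, the second rule would give 0.14 − 0.20 = −0.06. It is a bound, not a correction.

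**The case against.** The strongest reply is that the design already removes most of the motive. Every verified delivery pays USD 0.70 in both arms, so leaving out a non-attender costs the TBA money. A text sent before attendance is known or expected need not bias the proportion. The 0.37 is the only SD in the documents, and at that value even the 70% case does little harm. The protocol is open about its reliance on TBA reports and says that listing all mothers was beyond its budget. All of this stands, and it is why the point is a modest one.

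Three stronger readings are tempting, and the documents do not support them:

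- *That incentive-arm TBAs will hide non-attenders.* The flat fee makes this unprofitable. What remains is unequal effort over attenders, which is an inference and not something the documents show.
- *That intention-to-treat is the wrong label.* It is correct for TBAs analysed as randomised. What goes unstated is the set of clients in whom the outcome is measured.
- *That section 14.1 dismisses TBA under-reporting.* It concerns opt-out. Non-differential may also be meant as unrelated to outcome, in which case only its wording needs work.

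What survives is that no planned step can show which row of the table applies. Section 9.5 suggests that a community or women leader would probably know who had delivered, so an independent count in a subsample could measure omission directly. That would add field work, and the fix below does not depend on it.

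**Conclusion.** The point holds as a possible, unmeasured selection bias whose direction is conditional. At the protocol's SD of 0.37 it runs from negligible (+0.003) to small (+0.039), with at most about 10% false positives in the cases examined. Rates of 23% to 48% need both an assumed SD of 0.20 and a 30% loss of everyone except incentive-arm attenders.

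A reader might infer that selective reporting could account for a full 0.20 effect; that is unlikely. Even with one common rate, non-attenders would have to be reported at 0.375 (p = 20%) or 0.444 (p = 40%) times the rate of attenders. At SD 0.37, the 0.375 ratio gives only +0.024 or +0.107.

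Attendance, reporting completeness, the SD of 0.20 and the spread of deliveries are all assumptions. On the protocol's own SD this is a cheap improvement to the analysis plan, not a serious fault.

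**What to change.** 1. **SAP description and table.** Keep intention-to-treat for TBAs as randomised, and state that the outcome is measured among reported and verified clients. Compare reported, reached, refusing and verified clients per TBA by arm, and give the number of TBAs with no verified client. Note that equal totals do not rule out selection and that the count comparison has low power.
2. **SAP sensitivity analysis.** Refit the primary model with reported-but-unverified clients restored to the denominator. Count incentive-arm ones as not referred and give control-arm ones their TBA's observed proportion; as the extreme bound, count control-arm ones as referred. State a rule for control TBAs with no verified client. Do not count unverified clients as not referred in both arms, which can enlarge the bias. This uses observed counts and can move a TBA whose proportion is 1, but it does not reach women who were never reported.
3. **Optional, for unreported women.** Replace each incentive-arm y by y/(y + R(1 − y)) and report the R at which the confidence interval reaches 0, or that none in the range tried does. State that R cannot be estimated and that y = 0 or 1 does not move. At SD 0.37 and 20% attendance that is about 71% + 12% = 83% of TBAs, so a reassuring R should be read with caution.
4. **Protocol section 14.1.** Say that opt-out and contact will be compared by arm and that equal rates alone do not exclude bias.

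The cost is some SAP wording, one protocol sentence, call outcomes tabulated by TBA and arm, and a short added analysis. The headline becomes less tidy. No procedure or payment changes.
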